12 OCT 2020

## 5.7. Stopping Rules

This study may be discontinued at any time if, in the opinion of the DSMB, investigator, or Avalyn Pharma, continuation of the study represents a significant medical risk to participating patients. The DSMB will perform a safety data review after 20 patients have completed Week 4 and will make a recommendation at that time as to whether the study should continue or be modified. Avalyn Pharma also reserves the right to terminate the study at any time for any reason.

Avalyn Pharma, Inc.  
AP01-002

Protocol v2.1  
12 OCT 2020

## **6. STUDY SCHEDULE AND PROCEDURES**

### **6.1. Study Schedule**

The study schedule can be found in Tables 5 and 6. At-home patient assessments are outlined in Table 7. Detailed information on study assessments is provided in Section 7.

### **6.2. Study Visits**

Part A will consist of one Screening visit and 7 study visits, within the 24-week treatment period. Part B will consist of quarterly visits through study termination. A Follow-up visit will occur 28 days after the patient's End of Study visit in Part B.

#### **6.2.1. Visit 1 – Screening (Day -30 to Day -1)**

- Informed Consent
- Demography
- Medical history and concomitant medications including past 3 months
- Complete physical exam (PE) and vital signs, including height and weight
- Standard 12-lead ECG
- Saturated Oxygen (SaO2)
- Spirometry and DLCO
- Blood samples for laboratory tests (Chemistry including AST and ALT, Hematology)
- Urinalysis
- Urinary pregnancy test for females of childbearing potential (FOCBP) only
- Confirmation of IPF diagnosis as described in Section 5
- Inclusion/Exclusion Review

Leicester Cough Monitor (LCM) training. Patients that pass all of the screening criteria and are deemed eligible for the study will be provided with a LCM between the Screening and Baseline visit to wear for 24 hours. Patients will bring the LCM with them to the site at the Baseline visit. Optionally, patients may return to the clinic one day prior to the Baseline visit to receive their LCM and perform the 24-hour Baseline LCM reading; returning the LCM to the clinic the following day.

#### **6.2.2. Visit 2 - Baseline (Day 1)**

The following procedures will be conducted on Day 1 in chronological order:

- Cough Visual Analogue Scale (VAS), King's Brief Interstitial Lung Disease (KBILD) Questionnaire and Leicester Cough Questionnaire (LCQ)
- Concomitant medications since previous visit
- Record any AEs after signing informed consent
- Complete PE and vital signs

Avalyn Pharma, Inc.  
AP01-002

Protocol v2.1  
12 OCT 2020

- HRCT (If not performed at Screening or Screening HRCT was performed more than 1 month prior to Baseline. For scheduling purposes, the Baseline HRCT may be performed up to 1 month prior to or 1 week after the Baseline visit.)
- Pre-dose Spirometry and  $D_{LCO}$
- Pre-dose  $SaO_2$ ; Patients with  $SaO_2 < 90\%$  will be administered supplemental oxygen until the  $SaO_2$  reaches 93% prior to dosing
- Blood samples for laboratory tests (Chemistry including AST and ALT, Hematology, Biomarkers (CXCL13, CCL18, MMP3, CA19-9 and CA-125)
- Urinalysis
- Urinary pregnancy test (FOCBP only)
- Confirm Inclusion/Exclusion criteria
- Randomization
- Study material training and first study drug administration; patients experiencing excessive cough or bronchospasm will be administered 1 – 2 puffs (90 - 100  $\mu$ g) of salbutamol prior to subsequent doses or during initial dosing
- Post-dose Spirometry to be performed  $\leq 10$  minutes after completion of AP01 dose (Patients with a  $\geq 15\%$  drop from pre-dose spirometry who are symptomatic will be treated as described in section 8.6.)
- Post-dose  $SaO_2$
- Study material dispensation, including salbutamol and instructions for use of salbutamol (if needed as described in Sections 8.6 and 8.7.)
- Home spirometry training and dispensation

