#### *Diagnosis of IPF*

3. Clinical symptoms consistent with IPF of  $\geq 12$  months duration (with or without IPF diagnosis)
4. Diagnosis of IPF, defined as the first instance in which a patient was informed of having IPF, no more than 60 months before randomization.
  - Patients that have had an IPF diagnosis  $\geq 1$  year, the following criteria must be met:
    - HRCT and/or Surgical Lung Biopsy findings consistent with UIP. If honeycombing is not present on the HRCT, then one or both of the following criteria must be present:
      - Disease progression since diagnosis by HRCT and/or
      - An absolute loss of FVC  $\geq 5\%$  percent predicted over the past 12 months
  - Patients that have had IPF diagnosis within the last year, the following criteria must be met:
    - Diagnosis of Usual Interstitial Pneumonia (UIP) or IPF by HRCT (HRCT must be performed within 12 months prior to Screening) and/or Surgical Lung Biopsy as outlined in Table 4:

Avalyn Pharma, Inc.  
AP01-002

Protocol v2.1  

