**Notes for Tables 5 and 6:**

1. Follow-up visit will occur 28 days after the End of Study visit in Part B of the study.
2. A complete physical exam will be performed at Screening and Baseline visits. A modified physical exam including the patient's lungs and cardiovascular body systems will be performed at all other visits. For Safety Visits, only chest and skin exam are required.
3. Height is collected at the Screening visit only.
4. Blood samples for laboratory tests include: Chemistry (including AST and ALT), Hematology and Biomarkers (Blood samples for biomarkers will not be collected at Screening.) For Safety Visits, only AST and ALT are required.
5. Females of childbearing potential are required to take a urinary pregnancy test at each visit except the Follow-up visit.
6. Patients that pass screening and are scheduled to be randomized will receive a LCM to be worn for 24 hours and returned to the site at the Baseline visit. LCM will be worn for 24 hours at Visits 5 and 8. A paper diary will also be dispensed to the patient to record activities during the 24-hour period.
7. HRCT scans will be performed at Visits 2 and 8. The Baseline HRCT may be skipped if the HRCT for eligibility was performed less than 1 month prior to the Baseline visit.
8. Study material dispensation will occur at Visit 8 for those patients participating in Part B of the study.
9. Patients will be assessed for eligibility to participate in AP01-005 at EOS/Visit 12. Those enrolling in AP01-005 will use EOS/Visit 12 as their AP01-005 Baseline visit.
10. Patients enrolling in AP01-005 will not participate in the Follow-up visit.
11. Patients awaiting site approval of AP01-005 only.

Avalyn Pharma, Inc.  
AP01-002

Protocol V2.1  

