### **8.6. Investigational Drug Administration**

Patients will be trained on use of the eFlow and administration of the study drug at the Baseline visit. The first dose of study drug for each patient will be administered and observed at the clinical study site at the Baseline visit to confirm tolerability. All subsequent doses will be administered by the patient at home. All doses must be taken at least 4 hours apart.

Patients who experience cough that limits their ability to complete dosing will be given 1 – 2 puffs (90 - 100 µg) of an inhaled beta 2 agonist, such as salbutamol, in order to complete the in-clinic dose. These patients, as well as patients with a history of asthma or smoking history of 20 pack years or greater, or patients that have a  $\geq 15\%$  drop in FEV1 percent predicted in their pre-dose and post-dose readings and are symptomatic will be provided with and required to use 1 - 2 puffs (90 - 100 µg) of salbutamol prior to their second dose and for dosing throughout the study, unless these patients are currently taking a long-

Avalyn Pharma, Inc.  
AP01-002

Protocol V2.1  

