All relevant patient data will be included in listings. All patients entered into the database will be included in patient data listings.

Pulmonary function tests (PFTs) (including D_{LCO}) are performed at each study visit.

The following PFTs will be performed at all visits (including Screening) using spirometry (and documented on the PFT eCRF form):

- FVC Liters (L)
- FEV₁ Liters (L)
- % Predicated FVC
- % Predicted FEV₁.

Pre-dose and post-dose spirometry will be performed at the Baseline visit.

At every visit, D_{LCO} ($\text{mL}/\text{min}^{-1}/\text{mmHg}^{-1}$) and % Predicted D_{LCO} will be obtained using the site's standard methodology.

FEV₁/FVC ratio will be derived as: $100 \times \text{FEV}_1/\text{FVC}$.

For comparisons to baseline, data from Visit 2 prior to the first dose of study drug will be used as baseline, unless otherwise noted. For PFTs, the pre-dose result will be used as baseline. Subgroup analyses will be performed based on baseline groupings for FVC, region, age, sex, D_{LCO} and progression-related biomarkers (CXCL13, CCL18, MMP3).

If either regimen is eliminated based on Part A outcomes, patients may be switched to the selected regimen for the remainder of their participation. Data summaries will be created to mimic this switch by using the following treatment grouping for Part B: (1) randomized to 100 mg twice daily; (2) randomized to 50 mg once daily and stayed on 50 mg once daily; (3) randomized to 50 mg once daily and switched to 100 mg twice daily; (4) randomized to 50 mg once daily total [groups 2 and 3 combined]; (5) overall total for Part B data. Descriptive within-patient analyses will be included for those patients who switch from 50 mg once daily to 100 mg twice daily. These analyses will include spider plots of change from baseline showing when the dose switch took place. Data listings will include a variable to denote the regimen switch and flag the time of the switch for affected patients.

No formal hypothesis tests are planned.

This document is confidential.

SAP Version: 3.0 (15JUL2021)
Controlled Document ID: **3903A.01**, Effective Date 29-Oct-2018
Filing requirements: TMF

Page 22 of 52

Statistical Analysis PlanSponsor: Avalyn Pharma, Inc.; Protocol No.: AP01-002

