6.2.3. Baseline and Change from Baseline

Baseline is defined as the last non-missing measurement prior to or on the first dose of study drug.

Change from baseline = (post-baseline value – baseline value). For the purpose of tabulations, the unscheduled post-baseline values generally will be excluded.

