8.2.4. Change from baseline in cough severity as measured by VAS

The European Respiratory Society Cough Severity VAS⁶ will be completed at Baseline, all subsequent visits and the Follow-up visit. This is a paper-based scale that will be completed by the patient at the relevant visits. The scale will range on a vertical line from 'No Cough' at the bottom to 'Worst Cough Ever' at the top. The patient will put a cross on the line to indicate the severity of their cough in the last 2 weeks. The results of the scale will be measured in millimeters from the bottom of the scale to the marked cross and entered into the appropriate eCRF. Appendix Section 14.1 presents an example of the Cough Severity VAS.

The following statistics for Cough VAS will be calculated and summarized by treatment group and presented in a table:

- Summary statistics of the Cough Severity VAS score at Baseline and at each post-Baseline time point (Week 4, 8, 12, 16, 20, 24, 36, 48, 60, 72 and Follow-Up)
- Summary statistics of the Cough Severity VAS score reflecting the absolute change from Baseline to each post-Baseline time point (Week 4, 8, 12, 16, 20, 24, 36, 48, 60, 72 and Follow-Up).

The following plot will be produced for the Cough Severity VAS:

- Mean Cough Severity VAS Change from Baseline (\pm SD) vs. Visit Week (Week 4, 8, 12, 16, 20, 24, 36, 48, 60, 72 and Follow-Up) with lines for each treatment group.

All Cough Severity VAS score data will be presented in a listing.

8.2.5. Change from baseline in extent of fibrosis and lung volumes as assessed by HRCT

HRCT scans will be obtained to measure the extent of fibrosis and lung volumes at the Baseline visit and the Week 24 visit, or at an early termination visit if the patient does not complete Part A. These scans will be read and interpreted by a central reader.

The following statistics from the HRCT scans will be calculated and summarized by lung region and treatment group and displayed in a table:

- Summary statistics of the extent of fibrosis and lung volumes as assessed by HRCT at Baseline and the Week 24 post-Baseline time point, or separately for early terminations at the post-Baseline time point available.
- Summary statistics of the extent of fibrosis and lung volumes as assessed by HRCT reflecting the absolute change from Baseline to the Week 24 time point, or separately for early terminations at post-Baseline time point available.

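### The protocol allows a Baseline HRCT up to 1 week after first dose, but the SAP's baseline definition excludes it and makes no HRCT exception

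*Protocol*

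**What the plan says.** **Protocol.** Section 6.2.2 calls for an HRCT at Visit 2 "If not performed at Screening or Screening HRCT was performed more than 1 month prior to Baseline". To ease scheduling, it adds that "the Baseline HRCT may be performed up to 1 month prior to or 1 week after the Baseline visit". Note 7 under Tables 5 and 6 approaches the same point from the eligibility scan: "The Baseline HRCT may be skipped if the HRCT for eligibility was performed less than 1 month prior to the Baseline visit". Section 8.6 fixes when dosing starts: "The first dose of study drug for each patient will be administered and observed at the clinical study site at the Baseline visit".

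**SAP.** Section 6.2.3 gives the general definition: "Baseline is defined as the last non-missing measurement prior to or on the first dose of study drug". Section 6.1 gives a second one: "data from Visit 2 prior to the first dose of study drug will be used as baseline, unless otherwise noted". Section 8.2.5 states that "HRCT scans will be obtained to measure the extent of fibrosis and lung volumes at the Baseline visit and the Week 24 visit", adds an early-termination scan for patients who do not complete Part A, and sends these scans to a central reader. Its linear model takes change from baseline in whole-lung fibrosis and whole-lung volume as the outcome, with the baseline value and the timing of the HRCT among the covariates. Section 9.3 uses the baseline HRCT again, both as an absolute value and to form changes that are related to change in FVC.

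**The concern.** A scan on Days 2 to 8 is a proper Baseline HRCT under the protocol and a post-baseline measurement under the SAP. If the SAP definition is programmed as it stands, a patient who followed the protocol loses the baseline scan.

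The loss matters more for HRCT than for spirometry because the plan has only two scans per patient. Without the baseline scan there is no change score and no baseline covariate. SAP 6.3 does not impute values for summary tables and points to imputation only for the sensitivity analysis of the primary efficacy variable, so nothing would restore the patient to the HRCT change analyses. HRCT change is a listed secondary efficacy endpoint (SAP 4.2) and a stated objective (Protocol section 2).

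**Working it through.** The plan states no figure that depends on this point, so there is none to reproduce. The check is a comparison of the texts followed by date arithmetic.

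**1. Can a compliant scan follow first dose?** Yes. Dosing is on Day 1 and the window closes 1 week later: Day 1 + 7 days = Day 8. Days 2 to 8 are after first dose.

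**2. Does the SAP accept such a scan as baseline?** Not under 6.2.3 or 6.1. The last clause of the 6.1 sentence leaves room for exceptions, so I looked for one:
- 8.2.5 and 9.3, the HRCT sections, give none.
- 6.4 assigns follow-up data to visits by the eCRF and says that its windows do not apply in the baseline period. Its only HRCT rule is for Visit 8 in the Part A interim analysis (data up to 36 weeks).
- Section 12, on changes from the protocol, is silent on this.

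**3. What takes the scan's place?**
- *Nothing.* This is the likelier literal result. SAP 6.1 wants Visit 2 data, and SAP 8.2.5 and Protocol 7.3.2 describe central reading only for the Baseline and Week 24 (or early-termination) scans.
- *An earlier scan.* This needs quantitative values from an eligibility scan. Where a recent one exists, the Baseline scan is normally unnecessary, so the earlier scan would usually be more than 1 month old.

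**4. Intervals to the Week 24 scan.** Inputs: Visit 8 on Day 168 (Protocol Table 5), first dose on Day 1, no Day 0 (SAP 6.2.5). Assumptions: 1 month = 30 days and 12 months = 365 days.
- Planned: 168 − 1 = 167 days (23.9 weeks).
- Baseline scan on Day 8: 168 − 8 = 160 days (22.9 weeks), shorter by 7/167 = 4.2%.
- Earlier scan 31 days before Day 1: 31 + 167 = 198 days, 1.19 times planned.
- Earlier scan 12 months before a Screening visit 30 days ahead of Day 1: 365 + 30 + 167 = 562 days (80.3 weeks), 3.37 times planned.

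The last line uses the rule in Protocol 5.1 that the "HRCT must be performed within 12 months prior to Screening". That rule applies to patients diagnosed within the last year. For those diagnosed at least a year ago, the section states no age limit for the scan, so 562 days is not a limit for the trial.

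**5. Cost in precision.** The number of patients scanned on Days 2 to 8 is not given. As an assumption, if a fraction f of each arm drops out of the HRCT change model, the standard error of the between-arm difference grows by about 1/√(1 − f): 1.03 for f = 5%, 1.05 for 10% and 1.12 for 20%.

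**The case against.** The strongest reply is that an analyst would use the late scan anyway. The protocol itself names it the Baseline HRCT, SAP 8.2.5 speaks of the scan at the Baseline visit, and the eCRF would probably carry it as Visit 2. This is sensible and may well be what happens. It still contradicts SAP 6.2.3 as written, and the visit-assignment rule in 6.4 concerns follow-up data. What stands is that losing the scan follows from the literal text and is not inevitable.

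A second reply is that SAP 8.2.5 already adjusts for HRCT timing. That handles unequal intervals once a baseline exists, but it does not make a post-dose scan a baseline. Nor is it clear that time runs from the actual baseline scan, since the related plot takes weeks from visit dates.

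A third reply is that the scope is small: one secondary endpoint and its related correlations, in an unknown number of patients. This stands in full.

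On the other side, a reader might infer that affected patients will be given an eligibility scan up to about a year old, so that a 24-week change becomes one over about 80 weeks. The documents do not support that as the expected result. SAP 6.1 asks for Visit 2 data, nothing says that older eligibility scans are centrally read, and the protocol lets an eligibility scan stand in for the Baseline scan only when it is about 1 month old or less. The 80-week figure also rests on a limit that covers only recently diagnosed patients.

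**Conclusion.** The two documents conflict, and the SAP does not resolve it. Read literally, a patient whose Baseline HRCT falls on Days 2 to 8 most likely has no HRCT baseline and contributes nothing to the change analyses in SAP 8.2.5 and 9.3. In the absolute-value models of 9.3, only the baseline record would be lost. Use of an older scan is possible but less likely, and the documents set no trial-wide limit on the resulting interval.

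The overall effect cannot be sized because the number of such patients is unknown. For an affected patient, the choice is between losing the HRCT change entirely and accepting an interval that is at most 4.2% shorter than planned. The latter rests on the nominal Day 168 visit. The documents have no data on HRCT change in the first week of treatment, so a small bias from that week is an expectation and has not been shown.

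The primary FVC endpoint, the safety analyses and the sample size are unaffected. The point should be settled in the SAP, but it does not threaten the study's main conclusions.

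**What to change.** Add an HRCT-specific baseline rule to SAP 6.2.3 and refer to it in 8.2.5 and 9.3:
- Baseline is the last scan obtained within 1 month before, or on, the date of first dose.
- If there is none, baseline is the first scan up to 7 days after first dose.
- A scan more than 1 month before first dose is never baseline.
- HRCT time is measured from the actual date of the baseline scan.
- Baselines obtained after first dose are flagged and counted by arm, and a sensitivity analysis excludes those patients.

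This order matters. A rule that simply took the scan nearest Day 1 could choose an on-treatment scan when a pre-dose scan within the month was available.

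The cost is a few lines of SAP text, one flag and one extra run of the HRCT models, with no new data collection. A few baselines will include up to 7 days of treatment, which the protocol window already accepts. If Part A HRCT tables already exist, the report should state which scan served as baseline for these patients.

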### 6.2.3. Weekly Home Spirometry

Patients will perform home spirometry weekly during both Part A and Part B of the study. Home spirometry readings will be transferred electronically to the vendor.

### 6.2.4. Visit 2A

One week after the Baseline visit, the site will conduct a follow-up call to the patient to assess tolerability, study drug compliance, AEs, concomitant medications, status of the LCM return and use of the home spirometer.

### 6.2.5. Visits 3, 4, 5, 6, and 7 (Day 28, 56, 84, 112, 140 +/- 3 days, respectively)

The following procedures will be conducted at the listed visits in chronological order:

- Cough VAS, KBILD Questionnaire and LCQ
- AEs and concomitant medications since previous visit
- Modified PE (Lungs and Cardiovascular (CV) body systems only)
- Weight (Visit 5 only)

Avalyn Pharma, Inc.  
AP01-002

Protocol v2.1  
12 OCT 2020

- Vital signs
- SaO2
- Spirometry and DLCO
- Blood samples for laboratory tests (Chemistry including AST and ALT, Hematology, Biomarkers (CA19-9 and CA-125 only))
- Urinalysis
- Urinary pregnancy test (FOCBP only)
- LCM dispensation (Visit 5 only)
- Study material dispensation

#### **6.2.6. Visit 8 - End of Part A (Day 168 +/- 3 days)**

The following procedures will be conducted at the listed visits in chronological order:

- Cough VAS, KBILD Questionnaire and LCQ
- AEs and concomitant medications since previous visit
- Modified PE (Lungs and CV body systems only)
- Weight
- Vital signs
- SaO2
- Spirometry and DLCO
- Blood samples for laboratory tests (Chemistry including AST and ALT, Hematology, Biomarkers (CA19-9 and CA-125 only))
- Urinalysis
- Urinary pregnancy test (FOCBP only)
- HRCT
- LCM dispensation
- End of Treatment form for Part A completion
- Study material dispensation (3-month supply for patients participating in Part B only)

#### **6.2.7. Monthly Calls to Patient**

During Part B, the site will conduct a monthly call to the patient between visits to assess tolerability, study drug compliance, AEs, concomitant medications, status of the LCM return (when applicable) and use of the home spirometer.

#### **6.2.8. Visits 9, 10, and 11 – Part B (Day 252, 336, and 420 +/- 7 days, respectively)**

The following procedures will be conducted at the listed visits in chronological order:

- Cough VAS, KBILD Questionnaire and LCQ

Avalyn Pharma, Inc.  
AP01-002

Protocol v2.1  
12 OCT 2020

- AEs and concomitant medications since previous visit
- Modified PE (Lungs and CV body systems only)
- Weight (Visit 10 only)
- Vital signs
- SaO2
- Spirometry and DLCO
- Blood samples for laboratory tests (Chemistry including AST and ALT, Hematology, Biomarkers (CA19-9 and CA-125 only))
- Urinalysis
- Urinary pregnancy test (FOCBP only)
- Study material dispensation (3-month supply)

